# 9 STATISTICAL CONSIDERATIONS

## 9.1 Overview

[figure not shown]
5.1 Overview
Study CA059-001 is a multi-center, open-label, three-part, Phase 1, dose finding study to determine the safety, tolerability, PK, and PD of CC-95251 both alone and in combination with antineoplastic agents in subjects with R/R AML and R/R or treatment-naïve MDS or TN AML
The study will consist of dose escalation (Part A) and dose expansion (Parts B, C, and D).
to determine the preliminary RP2D o
CC-95251 both alone and in combination with azacitidine in R/R AML and R/R (IPSS-R
MDS subjects, and CC-99251 in combination with axacitidine and venetoclax in RR AML. Par
B further evaluates the safety and efficacy of CC-95251 alone and in combination with azacitidine
in R/R AML and R/R (IPSS-R MDS subjects. Part C evaluates the safety and efficacy o
CC-95251 in combination with azacitidine in treatment-naïve MDS (IPSS-R subjects. Par
D consists of a dose expansion in combination with injectable azacitidine and venetoclax (triple
combination) in subjects with TN AML ineligible for intensive chemotherapy. One or more dosing
regimens from Part A may be selected for cohort expansion in Parts B, C, and D
·
Data from all sites will be combined for the final analysis. Results will be presented using
descriptive statistics. Statistical analyses will be performed by drug combination and dose leve
(Part A) and by cohort (Parts B, C, and D) as needed or applicable. In the dose escalation (Part A
of the trial, summaries will be prepared by dose level and overall.
In the treatment-naïve MDS (IPSS-R
dose expansion (Part C) and treatment-naive AML dose expansion (Part D) of the trial, summaries
will be prepared by cohort and overall.
All analyses will be descriptive in nature. Summary tables for continuous variables will contain the following statistics of the corresponding seconds give many madien, standard deviation (SD)
the following statistics: n (the corresponding sample size), mean, median, standard deviation (SD) minimum (min), and maximum (max). Summary tables for categorical variables will include n
percentage, and confidence intervals on the percentage as appropriate
Unless otherwise indicated, confidence intervals for
omination into incidence,

## 9.2 Study Population Definitions

Table 13: Definition of study population

Population	Description
Enrolled	
Safety (all treated)	
Efficacy Evaluable (EE)	
Pharmacokinetic (PK) population	
Biomarker evaluable (BE) population	

[figure not shown]
Abbreviations: BE = biomarker evaluable; EE = efficacy evaluable; PK = pharmacokinetic.

[figure not shown]

Protocol CA059-001 Amendment 3.0 Final: 19 May 2023

recommended by the SRC.

DL1b is not tolerated in the CC-95251 plus azacitidine and venetoclax cohort, DL1b may be

## 9.4 Background and Demographic Characteristics

In Part A, the baseline characteristics of subjects will be summarized by drug combination and dose level for the enrolled population. In Parts B, C, and D the baseline characteristics of subjects will be summarized by cohort. Subject's age, height, weight, and baseline characteristics will be summarized using descriptive statistics, while sex, race and other categorical variables will be provided using frequency tabulations. Medical history data will be summarized using frequency tabulations by MedDRA system organ class and preferred term.

## 9.5 Subject Disposition

Subject disposition (analysis population allocation, ongoing, discontinued, along with primary reason) from treatment and study will be summarized using frequency and percent. A summary of subjects enrolled by site will be provided. Protocol deviations will be summarized using frequency tabulations. Supportive corresponding subject listings will also be provided.

# 9.6 Efficacy Analysis

The key efficacy variables are CRR (defined as CR + CRi + CRh for AML; CR for MDS) and ORR (all responses of CR [ie, CRMRD-, morphologic CR, CRh, CRi] + MLFS + PR for AML and CR + CRh + marrow CR + PR for MDS) by disease -appropriate response criteria. For dose expansion, efficacy variables to be analyzed include CRR and ORR, duration of remission, duration of response, stable disease rate (MDS only), relapse-free survival, event-free survival, progression-free survival, time to remission/response, transfusion independence, time to AML transformation for MDS subjects, and OS rates at 6 and 12 months. Point estimates and 2-sided 90% exact Clopper-Pearson confidence intervals of CRR and ORR will be reported. For time to event endpoints, Kaplan-Meier survival analyses will be performed. The PFS and overall survival rate will be measured and reported at pre-specified time points (ie, 6 months, 12 months).

Exploration of PK, PD, safety and activity relationships may be assessed.

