## **Overview of Key Efficacy Assessments**

Efficacy assessments include (Section 6.4):

- Clinical findings (eg, physical examinations, constitutional symptoms)
- Complete blood counts (CBC) and peripheral blood smears (PBS)
- Bone marrow examination (biopsy and/or aspiration)

Bone marrow (BM) aspiration and/or biopsy for disease burden assessments will be collected to
be evaluated for at Screening, end
of
In addition, bone marrow
aspirates (BMA) or biopsies (BMB) are performed to confirm CR or CRi or morphologic CR with
partial hematologic recovery (CRh), relapse after CR/CRi/CRh (as assessed by the Investigator
based on CBC with white blood cell [WBC] differential results), or disease progression. Additional
aspirates and/or biopsies will be collected as clinically indicated, based on Investigator's medical
judgement.

Complete blood count and peripheral blood smear (PBS) will be performed at the time of each bone marrow collection. Starting with subjects will be monitored for disease status using CBC and PBS for the second year or until progression of disease (or relapse).

Response to treatment will be assessed by Investigator using local laboratory results according to modified 2017 European Leukemia Network (ELN) AML Response Criteria (Döhner, 2017) for AML and modified International Working Group (IWG) Response Criteria (Cheson, 2006) for MDS. Hematologic response/transfusion dependence will also be evaluated. In addition, CRh will be reported for both AML and MDS (Bloomfield, 2018).

AML response criteria will be summarized by best overall response categories: complete remission rate (CRR) defined as CR + CRi + CRh, and objective response rate (ORR) defined as all responses of CR (ie, CRMRD-, morphologic CR, CRh, CRi) + MLFS + PR. For MDS, the complete remission rate (CRR) is defined as CR rate, objective response rate (ORR) includes all responses (CR + CRh + marrow CR + PR). The efficacy variable of focus will be complete remission rate (CRR) and ORR. Other measures of clinical activity include duration of remission, duration of response, stable disease rate (MDS only), relapse-free survival, event-free survival, progression-free survival (PFS), time to remission/response, transfusion independence, time to AML transformation for MDS subjects, and overall survival (OS) rates at 6 and 12 months.

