## **Table 2:** Study Objectives

## **Exploratory Objective(s)**

The exploratory objectives are:

- To explore the relationship between dose and systemic exposure of CC-95251 and measures of toxicity, efficacy, and PD biomarkers.
- To evaluate molecular and/or cellular biomarkers in the bone marrow and blood that may be associated with efficacy of CC-95251
- To evaluate the minimal residual disease (MRD) status, by flow cytometry and/or relevant gene sequencing methods

Abbreviations: ADA = anti-drug antibodies; AML = acute myeloid leukemia; MDS = myelodysplastic syndromes; MRD = minimal residual disease; PD = Pharmacodynamics; PK = pharmacokinetics.

**Table 3:** Study Endpoints

Endpoint	Name	Description	Timeframe
Primary	Safety	DLTs evaluated using the NCI CTCAE criteria, Version 5.0. Adverse events, including TEAEs, laboratory assessments, ECG results, ECOG performance status, and vital signs	Dose escalation and dose expansion  Screening to after the last dose of study treatment
Secondary	Preliminary efficacy a	Complete remission rate (CRR) (as assessed by the Investigator) for AML according to the modified European Leukemia Net (ELN) response criteria (CR + CRh + CRi), ORR (CR + CR MRD . + CRh + CRi + MLFS + PR)  CRR (as assessed by the Investigator) for MDS according to the modified IWG Response Criteria	Dose expansion Day 1 to end of follow up
		(CR), ORR (CR + CRh + marrow CR + PR)  Duration of remission, duration of response, stable disease rate (MDS only), relapse-free survival, event-free survival, progression-free survival, time to remission/response, transfusion independence, time to AML transformation for MDS subjects, OS rates at 6 and 12 months	
Secondary	Pharmacokinetics (PK)	Estimate parameters including but not limited to C max , C min , C trough , AUC (0-T) , AUC (TAU) , t max , CLT, and accumulation index of CC-95251, when feasible as a single agent and in combination with antineoplastic agents in AML and MDS	Dose escalation and dose expansion  Day 1 to 8 weeks post-dose of CC-95251
Secondary	Anti-drug Antibody (ADA)	Determine the presence and frequency of anti CC-95251 antibodies (ADAs) using a validated electrochemiluminescence (ECL) assay	Dose escalation and dose expansion  Day 1 to 8 weeks post-dose of CC-95251

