6.4 Efficacy Assessment
Blood and Bone Marrow Aspirate and/or Biopsy
Bone marrow (BM) aspiration and/or biopsy for disease burden assessments will be collected to
be evaluated for at Screening, end
In addition, bone marrow
aspirates (BMA) or biopsies (BMB) are performed to confirm complete remission (CR) or
morphologic CR with incomplete hematologic recovery (CRi) or morphologic CR with partial
hematologic recovery (CRh), relapse after CR, CRi, or CRh (as assessed by the Investigator based
on CBC with WBC differential results), or disease progression. Additional aspirates and/or
biopsies will be collected as clinically indicated, based on Investigator's medical judgement. Both
bone marrow aspirate and biopsy samples are mandatory at Screening
thereafter, a bone marrow aspirate alone is sufficient, but a biopsy must be collected if the aspirate
is not available and may be collected in addition to the aspirate per institutional practice.

Response to treatment will be assessed by Investigator using local laboratory results according to modified 2017 European Leukemia Network (ELN) AML Response Criteria (Döhner, 2017) for AML and modified IWG Response Criteria (Cheson, 2006) for MDS based on reported hematology laboratory parameters, peripheral blood smear, bone marrow aspirates and/or biopsies. Hematologic response/transfusion dependence will also be evaluated. In addition, CR with partial hematologic recovery (CRh) will be reported for both AML and MDS (Bloomfield, 2018).

AML response criteria will be summarized by best overall response categories: complete remission rate (CRR) defined as CR + CRi + CRh, and objective response rate (ORR, all responses of CR [ie, CRMRD-, morphologic CR, CRh, CRi] + morphologic leukemia free state [MLFS] + partial remission [PR]). For MDS, the CRR is defined as CR, ORR includes all responses (CR + CRh + marrow CR + PR). The efficacy variable of focus will be CRR and ORR. Other measures of clinical activity include duration of remission, duration of response, stable disease rate (MDS only), relapse-free survival, event-free survival, progression-free survival, time to remission/response, transfusion independence, time to AML transformation for MDS subjects, and overall survival (OS) rates at 6 and 12 months.

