#### Minimal residual disease

The minimal residual disease (MRD) response rate and MRD conversion rate will also be assessed as efficacy variables. MRD negative CR (CRMRD-), combined rate of CRs (cCRR = CR + CRMRD- + CRi + CRh in AML and CR + CRMRD- in MDS) will be assessed (Bloomfield, 2018).

MRD assessments will be performed in BMA or BMB at disease assessment timepoints using a flow cytometry-based and/or NGS-based method performed by central laboratory (refer to Biomarkers Section 6.6).

Testing for MRD will be performed locally, as applicable, per institutional guidelines in AML subjects with complete response in order to permit efficacy assessment according to ELN response criteria (Dohner, 2017).

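### Does the AML complete remission rate leave out MRD-negative complete remissions?

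*Combined protocol and SAP*

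**What the plan says.** The AML complete remission rate has the same three terms wherever it is defined. Section 9.6 has "The key efficacy variables are CRR (defined as CR + CRi + CRh for AML; CR for MDS", the Protocol Summary has "complete remission rate (CRR) defined as CR + CRi + CRh", and Section 6.4 and Table 3 agree. None of these places mentions MRD status.

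Other definitions name the MRD-negative state:

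- The same sentence of Section 9.6 gives "ORR (all responses of CR [ie, CR MRD -, morphologic CR, CRh, CRi] + MLFS + PR for AML".
- Table 3 sets the two formulas next to each other: "response criteria (CR + CRh + CRi), ORR (CR + CR MRD . + CRh + CRi + MLFS + PR".
- The MRD part of Section 6.4 adds a "combined rate of CRs (cCRR = CR + CR MRD - + CRi + CRh in AML and CR + CR MRD - in MDS".
- Table 19 (Appendix C) gives CRMRD- its own row and lists it beside CR in the stable-disease and hematologic-relapse rows.

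On measurement, Section 6.4 says "Response to treatment will be assessed by Investigator using local laboratory results". It also says "Testing for MRD will be performed locally, as applicable, per institutional guidelines in AML subjects with complete response", while MRD at the disease assessments uses a "flow cytometry-based and/or NGS-based method performed by central laboratory".

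**The concern.** In AML, cCRR equals the CRR terms plus CRMRD-. If CR already contains CRMRD-, cCRR duplicates CRR and the extra addend in the Table 3 ORR is redundant. A reader who expects each term to do some work may therefore conclude that CR in the CRR formula means CR other than MRD-negative CR. The umbrella phrase used for ORR does not settle this, because it also covers CRi and CRh, which CRR lists separately. AML response is summarized by best overall response category, so a programmer who coded CRMRD- as its own category and applied the three-term formula literally would leave those patients out.

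Two unwelcome effects would follow. A deeper remission would lower the reported CRR. The rate would also depend on whether a site tests for MRD locally, since the Investigator assesses response on local results. Central testing would narrow that dependence but not remove it. CRR is one of two key efficacy variables, so the question deserved a check.

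**Working it through.** **Plan figure.** The readable text gives no planning value, power or cohort size for CRR, so there is nothing to reproduce for this endpoint. The interval routine used below was checked on the composite CR cited in Section 1.2.3: 190/286 = 66.4% (190 inferred from 66.4% of 286), with an exact 95% interval of 60.6% to 71.9%, as printed there.

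**Definitions side by side.**

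1. The abbreviations under Table 3 and in Appendix A define CRMRD- as a morphologic CR in which MRD is absent. By definition it is a kind of CR.
2. In Table 19, morphologic CR and CRMRD- share the limits neutrophils ≥ 1,000/µL, platelets ≥ 100,000/µL, marrow blasts < 5% and no extramedullary disease. CRMRD- adds a negative marker. A patient who meets the second row therefore meets the readable part of the first (one of its cells is partly broken).
3. Local MRD testing is described for AML subjects who already have a complete response. MRD status qualifies a remission already established.
4. The listed terms are not disjoint elsewhere in Table 19. A patient with neutrophils of 700/µL and platelets of 120,000/µL, otherwise in CR, fits CRi (neutrophils < 1,000) and also CRh (> 500 and > 50,000). A full CR also meets the CRh count limits. The plus signs have to be read as any of these states, each patient counted once.

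Under this nested reading, CRR loses nothing, whatever the MRD-negative share or the extent of testing.

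**Size under the other reading.** Let f be the MRD-negative share of CRs and t the share of CR patients at sites that test. Both are assumptions. Under exclusive coding:

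loss = f × t × CR rate.

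| CR rate cited in the protocol | t | f = 0.25 | f = 0.50 | f = 0.75 |
|---|---|---|---|---|
| 36.7%, untreated AML (Section 1.4.1) | 1 | 9.2 | 18.4 | 27.5 |
| 36.7%, untreated AML | 0.5 | 4.6 | 9.2 | 13.8 |
| 19%, R/R AML (Section 1.2.3) | 1 | 4.8 | 9.5 | 14.3 |

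Entries are percentage points; for example 0.50 × 1 × 36.7 = 18.35. Both CR rates belong to other regimens. One recoded patient moves CRR by 100/n points: 5.0, 3.3 or 2.5 for assumed cohorts of 20, 30 or 40.

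**Example with the planned 90% exact interval.** Assume n = 30, with 18 complete remissions of any kind, 7 of them CRMRD-.

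- Nested: CRR = 18/30 = 60.0% (43.4 to 75.0).
- Exclusive: CRR = 11/30 = 36.7% (22.1 to 53.3).
- cCRR = 18/30 = 60.0% under either coding, since (11 + 7)/30 = 18/30.

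The 60% response and the count of 7 are assumed. With n from 20 to 40 and about 20% to 60% of remissions MRD-negative, the gap runs from 2/20 = 10 points to 11/30 = 37 points. The full complete-remission rate stays available as cCRR throughout.

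**The case for a change.** The strongest argument for a change is that inferring intent from definitions is not a derivation rule. No readable sentence says that CR counts regardless of MRD status, Table 3 prints CR and CRMRD- as two addends next to a CRR that has only one of them, and a clarifying clause would cost almost nothing. The textual observation is correct and stands.

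What does not stand is the step from there to a defective CRR. A redundant cCRR, which appears only in the MRD part of Section 6.4, is weak evidence that the plan meant to remove the best remissions from a key rate. Table 3 also attaches a footnote a to this efficacy row. Its text is not readable in the available copy and may cover the point, so a gap cannot be asserted with confidence. The point losses above apply only to the reading that the definitions disfavour, rest on assumed shares, and should not be taken as an expected effect.

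For MDS there is almost nothing to answer. Table 21 (Appendix E) has no CRMRD- row, so no MDS remission can be recoded out of CR under those criteria.

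**Conclusion.** The concern does not call for a change. The plan omits an explicit statement, but its own definitions make MRD-negative CR a subset of CR. An analyst applying Table 19 would count those patients, and CRR is then sound as written, with a loss of zero. Losses of roughly 5 to 28 points arise only under mutually exclusive coding, with assumed MRD-negative shares of 25% to 75%, assumed testing at half or all of the sites, and CR rates borrowed from other regimens.

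Even then no information would be lost. cCRR gives the complete-remission total, AML ORR names CRMRD- and is unaffected, and Section 9.9.6 reports the CRMRD- rate with a 95% interval. CRR is a secondary endpoint in an analysis that is descriptive throughout. A clause on MRD status would be harmless editing at a later amendment, but no result depends on it, and removing cCRR is not needed. The conclusion rests on the readable text, with the Table 3 footnote unseen.

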#### Progressive disease for AML will be defined as:

- A > 50% increase in bone marrow blast count percentage from the baseline (screening) bone marrow blast count (a minimum 15% point increase is required in cases with <30% blasts at baseline; or persistent bone marrow blast count > 70%, over at least 3 months; without at least a 100% improvement in ANC to an absolute level (> 0.5 x 10^9/L) and/or platelet count > 50 x 10^9/L non-transfused), or
- A > 50% increase in peripheral blasts (WBC × % blasts) to > 25 x  $10^9/L$  (> 25,000/ $\mu$ L) (in the absence of differentiation syndrome), or
- New extramedullary disease.

The date of progressive disease is defined as the first date that there was either a > 50% increase in BM blast count from baseline, a persistence of BM blasts > 70% in subjects with a baseline BM blast count of > 70%, or a doubling of the peripheral blood (PB) blast count.

Treatment failure will be defined as progressive disease or not achieving at least partial remission (PR) by the end of the treatment period. Subjects may continue treatment if they are deriving benefit from treatment without unacceptable toxicity (any CR, MLFS, PR, or SD with demonstrated clinical benefit eg, reduction in transfusion burden), as judged by the Investigator, or until disease progression, loss of clinical benefit, unacceptable toxicity, or decision to withdraw by subject or Investigator. Failure to achieve a response while simultaneously not meeting the criteria for progressive disease will be considered stable disease.

Subjects who discontinue study treatment for reasons other than disease progression (or relapse) or start of a new anticancer therapy will have disease assessments according to the specified

assessment schedule (refer to Section 6.3.2) until progression (or relapse) and/or initiation of new anticancer therapies. For subjects who have discontinued study treatment due to relapse or progression or start of a new anticancer therapy, follow up can be performed by site visits or phone calls. Subjects will be followed they have died, are lost to follow up, withdraw consent for further data collection, or until study closure.

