## APPENDIX E RESPONSE CRITERIA FOR MYELODYSPLASTIC SYNDROMES (MDS)

The revised recommendations of the International Working Group (IWG) for diagnosis, standardization of response criteria, treatment outcomes, and reporting standards for therapeutic trials in myelodysplastic syndromes (MDS) modified for this protocol.

Table 21: Modified IWG Response Criteria for MDS

Category	Response criteria (responses must last at least 4 weeks)			
Complete remission (CR)	Bone marrow: $\leq$ 5% myeloblasts with normal maturation of all cell lines a Persistent dysplasia will be noted a,b Peripheral blood c - Hemoglobin $\geq$ 11 g/dL  - Platelets $\geq$ 100 $\times$ 10  /L  - Neutrophils $\geq$ 1.0 $\times$ 10  /L b - Blasts 0%			
Morphologic CR with partial hematologic recovery (CRh)	Bone marrow: $\leq 5\%$ myeloblasts with normal maturation of all cell lines a Persistent dysplasia will be noted a,b Peripheral blood c - Hemoglobin $\geq 11$ g/dL  - Platelets $> 50 \times 10^9$ /L  - Neutrophils $> 0.5 \times 10^9$ /L b - Blasts $0\%$			
Partial remission (PR)	All CR criteria if abnormal before treatment, except:  Bone marrow blasts decreased by $\geq 50\%$ over pretreatment but still $> 5\%$ Cellularity and morphology not relevant			
Marrow CR b ± Hematologic Improvement (HI)	Bone marrow: ≤ 5% myeloblasts and decrease by ≥ 50% over pretreatment b Note: Blasts at baseline must be ≥ 5% in order for subject to be evaluable for Marrow CR d Peripheral blood: if HI responses, they will be noted in addition to marrow CR b			
Stable disease (SD)	Failure to achieve at least PR, but no evidence of progression for >			
Failure	Death during treatment or disease progression characterized by worsening of cytopenias, increase in percentage of bone marrow blasts, or progression to a more advanced MDS FAB subtype than pretreatment			
Relapse after CR or PR	At least 1 of the following:			
	
 
Return to pretreatment bone marrow blast percentage
 
Decrement of ≥50% from maximum remission/response levels in granulocytes or platelets
 
Reduction of Hgb concentration by ≥ 1.5 g/dL or transfusion dependence
 
			
Cytogenetic Response	Complete – Disappearance of the chromosomal abnormality without appearance of new ones  Partial – At least 50% reduction of the chromosomal abnormality			

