Disease Progression (PD)	For subjects with:  • Less than 5% blasts: ≥ 50% increase in blasts to > 5% blasts  • 5% - 10% blasts: ≥ 50% increase in blasts to > 10% blasts  • 10% - 20% blasts: ≥ 50% increase in blasts to > 20% blasts  Any of the following:  • At least 50% decrement from maximum remission/response levels in granulocytes or platelets  • Reduction in Hgb concentration by ≥ 2 g/dL  • Transfusion dependence			

Table 21: Modified IWG Response Criteria for MDS

Category	Response criteria (responses must last at least 4 weeks)
Disease transformation	Transformation to AML (20% or more BM or PB blasts) d
Hematologic Improvement (HI)	
Erythroid response (HI-E)	Hgb increase by $\ge$ 1.5 g/dL
(Pretreatment < 11 g/dL)	Relevant reduction of units of RBC transfusions by an absolute number of at least 4 RBC transfusions. Compared with the pretreatment transfusion number in the previous only RBC transfusions given for a Hgb of $\leq 9.0$ g/dL pretreatment will count in the RBC transfusion evaluation
Platelet response (HI-P)	Absolute increase of $\geq 30 \times 10^9 / L$ for subjects starting with $> 20 \times 10^9 / L$
(Pretreatment $< 100 \times 10^{9}$ L)	Increase from $< 20 \times 10^9/L$ to $> 20 \times 10^9/L$ and by at least 100%
Neutrophil response (HI-N)	At least 100% increase and an absolute increase of $> 0.5 \times 10^9/L$
(Pretreatment $< 1.0 \times 10^9/L$ )	
Progression/relapse after HI	At least one of the following:
	At least 50% decrement from maximum response levels in granulocytes or platelets
	• Reduction in Hgb by ≥ 1.5 g/dL
	Transfusion dependence

Abbreviations: AML = acute myeloid leukemia; BM = bone marrow; CR = complete remission; FAB = French-American-British; Hgb = hemoglobin; HI = hematologic improvement; HI-E = HI - erythroid response; HI-P = HI - platelet response; HI-N = HI - neutrophil response; IWG = International Working Group; MDS = myelodysplastic syndromes; PB = peripheral blood; PD = Disease Progression; PR = partial remission; RBC = red blood cell; SD = stable disease.

- a Dysplastic changes should consider the normal range of dysplastic changes (modification).
- b Modification to IWG response criteria.

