### APPENDIX G FOR MDS

### REVISED INTERNATIONAL PROGNOSTIC SCORING SYSTEM

Table 23: IPSS-R Cytogenetic Risk Groups

Cytogenetic Prognostic Subgroups	Cytogenetic Abnormalities	
Very good	-Y, del(11q)	
Good	Normal, del(5q), del(12p), del(20q), double including del(5q)	
Intermediate	del(7q), +8, +19, i(17q), any other single or double independent clones	
Poor	-7, inv(3)/t(3q)/del(3q), double including -7/del(7q), Complex: 3 abnormalities	
Very poor	Complex: > 3 abnormalities	

Abbreviations: del = deletion; inv = inversion; IPSS-R = Revised International Prognostic Scoring System score; p = short arm of a chromosome; q = long arm of a chromosome; t = translocation.

Source: Greenberg, 2012.

Table 24: IPSS-R Prognostic Score Values

Prognostic variable	0	0.5	1	1.5	2	3	4
Cytogenetics	Very Good	-	Good	-	Inter- mediate	Poor	Very Poor
Bone Marrow Blast (%)	≤ 2	-	> 2 - < 5	-	5 - 10	> 10	-
Hemoglobin (g/dL)	≥10	-	8 - < 10	<8	-	-	-
Platelets (× 10  /L)	≥100	50 - < 100	< 50	-	-	-	-
ANC (× 10  /L)	≥0.8	< 0.8	-	-	-	-	-

Abbreviations: ANC = absolute neutrophil count; IPSS-R = Revised International Prognostic Scoring System score. Source: Greenberg, 2012.

The total IPSS-R score is calculated as the sum of the cytogenetics, bone marrow blast percentage, hemoglobin, platelets, and ANC individual scores.

Table 25: IPSS-R Prognostic Risk Categories/Scores

Risk Category	Risk Score
Very Low	≤1.5
Low	> 1.5 – 3
Intermediate	> 3 – 4.5
High	> 4.5 - 6
Very High	> 6

Abbreviations: IPSS-R = Revised International Prognostic Scoring System score.

Source: Greenberg, 2012.

Protocol CA059-001 Amendment 3.0

Table 26: IPSS-R: Prognostic Risk Category Clinical Outcomes

Prognostic variable	No. pts	Very Low	Low	Intermediate	High	Very High
Subjects, %	7012	19%	38%	20%	13%	10%
Median Overall Survival (years)	-	8.8	5.3	3.0	1.6	0.8
Median time to 25% AML evolution	-	Not reached	10.8	3.2	1.4	0.73

Abbreviations: AML = acute myeloid leukemia; IPSS-R = Revised International Prognostic Scoring System score. Source: Greenberg, 2012.

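### Time to AML transformation falls under a blanket Kaplan-Meier rule although death without AML is a competing event: use cumulative incidence, or name the curve AML-free survival (minor)

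*Combined protocol and SAP*

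**What the plan says.** Section 9.6 ends its list of dose-expansion efficacy variables with "time to AML transformation for MDS subjects, and OS rates at 6 and 12 months". Soon after comes the only method statement for this kind of endpoint: "For time to event endpoints, Kaplan-Meier survival analyses will be performed". The Statistical Methods part of the Protocol Summary says the same. Table 3 places the endpoint among the secondary efficacy endpoints ("time to AML transformation for MDS subjects, OS rates at 6 and 12 months").

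Appendix E, Table 21 describes disease transformation as "Transformation to AML (20% or more BM or PB blasts"). Death appears in a different row of that table, Failure: "Death during treatment or disease progression characterized by worsening of cytopenias".

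The Overview of the statistical section says that all analyses are descriptive and that summaries for the treatment-naïve MDS expansion (Part C) "will be prepared by cohort and overall". Section 6.4 adds that, for subjects who stop treatment for other reasons, disease assessments continue "until progression (or relapse) and/or initiation of new anticancer therapies"; Section 6.3.2 is to the same effect. Section 6.3.3 follows all subjects for survival after the end of treatment.

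No readable passage says how a death without transformation enters this endpoint, and none names a cumulative-incidence method. The notes to Table 3 and the definitions in Table 13 are partly or wholly lost in the public copy.

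**The concern.** By the definition in Table 21, death is not a transformation, yet it ends the chance of one. It is therefore a competing event, and Kaplan-Meier leaves two ways to treat it:

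- **Deaths censored.** 1-KM then estimates the risk of AML as if nobody could die first. It is higher than the proportion of subjects who actually transform.
- **Deaths counted as events.** Kaplan-Meier is then valid, but for AML-free survival. Under the label of time to AML transformation, that curve would be misread.

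What is at stake is the meaning of a reported curve in the MDS expansion cohorts. The same label could cover two quite different numbers, and a reader who sets the result beside other data needs to know which one is shown.

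**Working it through.** The documents give no transformation rate or expected figure for this endpoint, so there is no plan figure to reproduce. The sums below only show scale, and only for Part C.

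**Inputs from Appendix G, Table 26** (Intermediate, High, Very High)
- Median overall survival: 3.0, 1.6, 0.8 years.
- "Median time to 25% AML evolution": 3.2, 1.4, 0.73, read as years.
- Share of subjects: 20%, 13%, 10%, used as pooling weights 20/43, 13/43, 10/43. The IPSS-R cut-off is blacked out, so this mix is an assumption.

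**Hazards per year, assumed constant**
- Transformation, a = -ln(0.75)/t25: 0.0899, 0.2055, 0.3941.
- Overall death, D = ln(2)/median: 0.2310, 0.4332, 0.8664.
- Death without AML, d: not given in the documents. AML-free survival cannot exceed overall survival, so a + d must be at least D. The lower limit is d = D - a = 0.1411, 0.2277, 0.4723, that is 61%, 53% and 55% of D. The upper limit is taken as d = D.

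The lower limit matters. At d = 25% of D, a + d would be 0.148, 0.314 and 0.611, below D in every group. AML or death would then reach 25.2% at 12 months against pooled mortality of 33.7%, which is impossible.

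**Formulas at time t**
- 1-KM with deaths censored, one group: 1 - exp(-a·t).
- Cumulative incidence, one group: a/(a+d) · [1 - exp(-(a+d)·t)].
- Deaths as events, one group: 1 - exp(-(a+d)·t).
- Pooled cumulative incidence and pooled deaths-as-events are weighted means. Pooled 1-KM is 1 - exp(-∫h), with h(u) = Σ w·a·exp(-(a+d)u) / Σ w·exp(-(a+d)u).

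**Results at 12 months (%)**

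| | d = D - a | d = D |
|---|---|---|
| Cumulative incidence, Intermediate / High / Very High | 8.03 / 16.68 / 26.36 | 7.69 / 15.19 / 22.40 |
| Pooled cumulative incidence | 14.9 | 13.4 |
| Pooled 1-KM | 16.6 | 16.1 |
| Gap (points) | 1.7 | 2.7 |
| Pooled, deaths as events | 33.7 | 43.7 |

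Check on the pooled cumulative incidence at d = D - a: (20 × 8.03 + 13 × 16.68 + 10 × 26.36)/43 = 14.9. At 6 months the pooled pairs are 8.99 vs 8.49 and 8.84 vs 7.99, a gap of 0.5 to 0.9 points.

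**Second reading of Table 26.** If the 25% times are quantiles of cumulative incidence, a solves a/(a+d) · [1 - exp(-(a+d)·t25)] = 0.25. The pooled 12-month pairs become 19.3 vs 17.6 (lower limit) and 21.7 vs 18.1 (d = D), a gap of 1.7 to 3.6 points. Deaths as events then reach 47.2% at d = D.

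**Cross-check.** An illness-death model fitted to the same median survival, with assumed median survival after AML of 3, 6 or 12 months, gives gaps of 2.0 to 3.2 points over both readings.

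**Sampling error.** Cohort sizes are blacked out. If n is 20 to 40, the 95% half-width at 16% is 1.96 × √(0.16 × 0.84/n) = 16.1 to 11.4 points.

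**The case against.** The strongest reply has four parts.

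- **The method sentence is generic.** It does not single out this endpoint, and Section 9.6 promises figures at 6 and 12 months only for PFS and overall survival. That is so: no 12-month transformation probability is a stated output. But the endpoint is in the list that the sentence serves, and no other method is offered for it.
- **Table 21 defines a response category, not the time-to-event variable.** The lost text may define the endpoint as AML or death, for which Kaplan-Meier is sound. This stands, and it reduces that branch to a matter of naming. It does not rescue the other branch.
- **The effect is immaterial.** A gap of 2 to 4 points lies well inside a half-width of 11 to 16 points, and the endpoint is secondary and descriptive. This also stands, and it sets the weight of the point.
- **Table 26 is prognostic data, not data on subjects given azacitidine with the study drug.** True, so the figures show scale and predict nothing.

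A reader might go further and infer a large bias. In the Very High group the 12-month gap is 6.2 to 10.2 points (32.6% vs 26.4% to 22.4%), and pairing the 4.5-month median survival quoted for relapsed MDS in Section 1.1.2 with Table 26 transformation times gives up to 16.9 points. The documents do not support that as a finding: no curves by risk group are visibly planned, and Table 26 does not describe relapsed or refractory disease, so no figure can be claimed for Part B. Nor may a reader infer that the plan censors deaths or has no rule for them; the readable text is silent on this.

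**Conclusion.** The point holds as a minor one. A blanket Kaplan-Meier rule covers an endpoint for which, by the protocol's own definition of transformation, death is a competing event. Under either treatment of deaths, the curve is not the probability of transformation.

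For Part C, pooled over Intermediate to Very High risk, 1-KM with deaths censored would be about 16.1% to 16.6% at 12 months against a cumulative incidence of 13.4% to 14.9%; under the second reading of Table 26, 19.3% to 21.7% against 17.6% to 18.1%. Counting deaths as events gives about 34% to 44%, or up to 47%. The distance between these two treatments is far larger than the bias within the first, so clear labelling matters more than the few points of overstatement. All these figures rest on constant hazards, Table 26 prognosis, the 20:13:10 mix, and a death-without-AML hazard between D - a and D.

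Nothing visible in dose selection, stopping, CRR or ORR depends on this endpoint.

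**What to change.** In Section 9.6 and the Protocol Summary, state that time to AML transformation is estimated by the Aalen-Johansen cumulative incidence, with death without transformation as a competing event. If AML-free survival is what is meant, keep Kaplan-Meier and give the endpoint that name. Reporting both is also reasonable.

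In the same place, say how subjects are handled when disease assessments stop at progression without AML or at a new anticancer therapy. Aalen-Johansen does not remove informative censoring from that source, so the limitation should be noted with the result.

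The cost is a few lines of text and a standard procedure. Survival follow-up of all subjects is already planned, so deaths are being collected. The reported curve will lie slightly below a death-censored 1-KM curve.
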